## 5.3 Other Efficacy Analyses

The analyses of the secondary efficacy endpoints at Week 24 in Section 5.2 will also be performed for all other applicable visits.

## 5.4 Subgroup Analyses for Efficacy Endpoints

The primary and secondary efficacy endpoints will be summarized with descriptive statistics by baseline fibrosis stage (F2 or F3) and by baseline statin use (experienced or naive). No inferential statistics will be provided for the subgroups.

## 6. Safety Analyses

## 6.1 Study Treatment Exposure and Compliance

## 6.1.1 Exposure to Study Treatment

Treatment exposure duration will be calculated as the date of the last dose of study drug minus the date of first dose of study drug plus one day. Treatment exposure duration will be summarized with descriptive statistics by treatment group. In addition, the number and percentage of subjects with treatment exposure duration of the following categories will be summarized by treatment group: <2 weeks, 2 to <4 weeks, 4 to <8 weeks, 8 to <12 weeks, 12 to <16 weeks, 16 to <20 weeks, and 20 to <24 weeks, etc.

## 6.1.2 Study Treatment Compliance

Study treatment compliance is defined as the number of injections actually administered (i.e., number prescribed – number returned) by a patient during the 24-week period divided by the number of injections prescribed multiplied by 100. Descriptive statistics for study treatment compliance will be presented by treatment group. In addition, the number and percentage of subjects with treatment compliance of the following categories will be summarized by treatment group: <80%, 80% to 100%, and >100%.

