Subjects to be studied will have histologically confirmed NASH as defined by the NIH NASH CRN (Kleiner 2005) and determined by a qualified central pathologist's reading (see [Appendix 1](#)). Historical biopsy results within 6 months of the first Screening visit may be used for inclusion into the study; otherwise, a liver biopsy must be obtained for assessment. Subjects must have a NAS of at least 4, with a minimum of 1 point in each of the three components, along with the presence of either Stage 2 or 3 fibrosis. Subjects with no (Stage 0) or minimal (Stage 1) fibrosis and cirrhosis (Stage 4) will be excluded from this study. Subjects will undergo MRI during the Screening period, which must demonstrate $\geq 8\%$ total liver fat content (LFC) by MRI-PDFF.

Subjects may be rescreened once with Medical Monitor approval. Note: certain laboratory parameters of interest (e.g., AST, TBL, creatinine clearance) may be retested at the investigators' discretion after discussing with the Medical Monitor.

On Day 1, eligible subjects will be randomized into one of the four treatment groups (0.3 mg aldafermin, 1 mg aldafermin, 3 mg aldafermin, or placebo) in a 1:1:1:1 ratio ([Table 3](#)). Randomization will be stratified by baseline stage of fibrosis (Stage 2 versus 3) on the qualification liver biopsy as determined by the Central Pathologist. Treatment assignment will be blinded to the investigational sites, study subjects, and sponsor (both Study Team and sponsor Medical Monitor or designee) throughout the study period and managed [REDACTED]. Study-drug self-administration instructions and training will be provided to the subjects and study-drug kits will be dispensed.

Table 3. Study Design

Study Treatment Group	Dose of aldafermin ^[1]	Mode of Administration	Volume of Injection ^[2]	Number of Subjects Planned
A	0.3 mg			38
B	1 mg			38
C	3 mg			38
D	Matched-Placebo			38
Total number of Subjects Planned:				152

^[1] In clinic dosing will occur on Day 1 and Study Week 2, 4, 8, 12, 18, and 24.

^[2] Presented in single-use prefilled syringes.

The first dose of aldafermin (Day 1) and doses at Weeks 2, 4, 8, 12, 18, and 24 study visits will be self-administered in the clinic, with all other daily doses through Week 24 self-administered at home. Self-administration should occur daily at a similar time at home. Subjects will return to the clinic on Weeks 2, 4, 8, 12, and 18 for on-treatment assessments and to receive aldafermin study-drug kits.

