9.1 Schedule of Study Procedures

The Schedule of Study Procedures is shown in [Table 4](#). The visits should occur as close to the intended dates as possible. However, Weeks 2 and 4 will have a visit window of ± 3 days. Weeks 8, 12, 18, and 24 will have a visit window of ± 7 days. Week 25 will have a visit window of $+3$ days, and Week 30 will have a visit window of ± 7 days. Subjects attending any visits out of windows from Day 1 to Week 24/Early Withdrawal (EOT) visit should be brought back into compliance with the overall study-visit schedule as soon as possible thereafter. Subjects will return to the clinic at Week 25 and Week 30 (1 and 6 weeks after last dose) for a post-treatment response and EOS follow-up visits, respectively.

Subjects who have an LDL-C value of > 100 mg/dL and > 15 mg/dL above their Day 1 value at Week 25 will need to be re-assessed at Week 30. Subjects who have an LDL-C value of > 100 mg/dL and > 15 mg/dL above their Day 1 value at Week 30 will have an additional 4- week follow up visit to confirm their LDL-C value is ≤ 100 mg/dL or ≤ 15 mg/dL above their Day 1 value. Subjects will continue to be followed until their LDL-C value is ≤ 100 mg/dL or ≤ 15 mg/dL above their Day 1 value. Subjects whose LDL-C values are not adequately managed by their maximum tolerated rosuvastatin dose plus ezetimibe will be discontinued from study and an early withdrawal study visit will be completed. The follow up/EOS visit should be scheduled for 6 weeks after the early withdrawal study visit.

Table 4. Schedule of Study Procedures

Study Procedure	(Screening) ^b	D -42	D -28 to -1	D1	W2	W4	W8	W12	W18	W 24/EW (EOT)	W25 (Post-Tx)	W30 (EOS)
Visit Window (Days) ^a					± 3	± 3	± 7	± 7	± 7	± 7	+3	± 7
Informed consent		X										
Demographics		X										
Medical history		X										
Smoking History		X										
Inclusion/exclusion criteria		X		X								
Height		X										
Body weight, BMI, waist circumference		X		X				X		X		X
		■		■	■	■	■	■	■	■	■	■
Alcohol Consumption ^c		X										
12-lead ECG		X		X				X		X		X
Vital signs		X		X	X	X	X	X	X	X		X
Central read of locally performed historical biopsy slides, if available		X										
MRI-PDFF ^d				X				X		X		X
Liver biopsy ^e				X						X		
				■								
Prior and concomitant medications		X	X	X	X	X	X	X	X	X	X	X
Adverse events ^f		X	X	X	X	X	X	X	X	X	X	X
LISSA evaluations				X	X	X	X	X	X	X		
Chemistry (fasted \geq 10 hrs)		X ^h	X ^h	X ^{g,h}	X ^g	X ^g	X ^g	X ^{g,h}	X ^g	X ^{g,h}	X ^g	X ^g

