10.4 Dose Preparation and Administration

10.4.1 Aldafermin

Subjects will be instructed to dose with aldafermin/matched placebo at home at a similar time each day. Study-drug/placebo syringes will be equilibrated to room temperature prior to use. Study-drug/placebo will be administered as a SC injection in the abdomen. On Day 1, subjects will be trained on self-administering a SC injection. During the on-treatment visits, self-administration will occur in the clinic under observation by clinic staff. Re-training will be provided as required. Written dose preparation and administration instructions will be provided to subjects. Subjects will be required to complete a daily study-drug/placebo administration diary.

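### The compliance formula in SAP 6.1.2 cannot exceed 100%, so its planned >100% category is always empty, and it misstates compliance for subjects who withdraw early

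*SAP*

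**What the plan says.** SAP 6.1.2 takes compliance to be "number of injections actually administered (i.e., number prescribed – number returned) by a patient during the 24-week period divided by the number of injections prescribed", expressed as a percentage. It then plans counts and percentages by treatment group in the categories "<80%, 80% to 100%, and >100" percent. The section does not say whether *prescribed* means syringes dispensed, doses planned for the whole 24 weeks, or doses scheduled up to discontinuation. It does not say how syringes that never come back are counted.

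The dosing background is in Protocol Section 7. The first dose and the doses on visit days are given in the clinic, "with all other daily doses through Week 24 self-administered at home". Kits are given out on Day 1 and later: "Subjects will return to the clinic on Weeks 2, 4, 8, 12, and 18 for on-treatment assessments" and to collect new kits. Under Protocol 9.1, the Week 2 and Week 4 visits have a window of 3 days either side, and "Weeks 8, 12, 18, and 24 will have a visit window of" 7 days either side. Protocol 9.2.4 to 9.2.9 have used kits and diaries collected and reconciled at visits, including the Early Withdrawal visit. Protocol 10.4.1 adds a second source: "Subjects will be required to complete a daily study-drug/placebo administration diary". The SAP formula does not use it.

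**The concern.** The definition and the table it feeds do not fit together. A fraction whose numerator is its own denominator minus a non-negative count cannot exceed one, yet the plan reserves a row for values above one. Either the formula or the row is wrong.

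The second problem is that the denominator is not tied to how long the subject was on treatment. Syringes left over because a subject stopped early are then treated like missed doses, or, on another reading, syringes never handed out are treated as injected. SAP 1.3 assumes 15% drop-out, about 23 of 152 subjects (0.15 × 152 = 22.8), so this is not a rare case.

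At stake is the reliability of one exposure table. SAP 6.1.1 reports duration as last dose date minus first dose date plus one. That shows early stopping but not gaps. In the readable text, compliance is the only planned summary that could show missed or extra doses between the first and last injection.

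**Working it through.** The plan gives no compliance figure to reproduce, so the check evaluates its formula.

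**Upper bound.** With P prescribed and R returned, C = 100 × (P − R)/P = 100 − 100 × R/P. Since R ≥ 0, the maximum is 100%, reached at R = 0. No assumption about the meaning of P is needed.

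**Inputs for worked cases.** Daily dosing from Day 1 through the Week 24 visit, split by dispensing interval: 14 + 14 + 28 + 28 + 42 + 43 = 169 doses, counting the clinic dose at Week 24. The cases assume exactly the nominal number of syringes per interval, with no spares.

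- Up to the Week 4 visit: 14 + 14 = 28 dispensed.
- After the Week 8 visit: 14 + 14 + 28 + 28 = 84 dispensed.
- After the Week 12 visit: 84 + 42 = 126 dispensed.

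**Early withdrawals under three readings of P.** The column *true* is doses taken divided by days to stopping.

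| Subject | Returned | P = dispensed | P = 169 | P = scheduled to stopping | True | Share of 169 |
|---|---|---|---|---|---|---|
| Adherent, stops at Week 4 after 28 doses | 0 | 28/28 = 100% | 169/169 = 100% | 28/28 = 100% | 28/28 = 100% | 28/169 = 16.6% |
| Adherent, stops Day 70 | 84 − 70 = 14 | 70/84 = 83.3% | 155/169 = 91.7% | 56/70 = 80.0% | 70/70 = 100% | 70/169 = 41.4% |
| Half the doses to Day 70 | 84 − 35 = 49 | 35/84 = 41.7% | 120/169 = 71.0% | 21/70 = 30.0% | 35/70 = 50% | 35/169 = 20.7% |
| Adherent, stops Day 90 | 126 − 90 = 36 | 90/126 = 71.4% | 133/169 = 78.7% | 54/90 = 60.0% | 90/90 = 100% | 90/169 = 53.3% |

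Whenever unused syringes come back, every reading gives a wrong value. The direction is not constant: the half-adherent subject is scored too high on the regimen reading and too low on the other two. In the Week 4 case the regimen reading gives 100% only because it credits 141 syringes that were never handed out (169 − 28). It agrees with on-treatment compliance by coincidence and is far from the 17% of the course received.

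If the Day 90 subject returns nothing, both the dispensed reading (126/126) and the regimen reading (169/169) give 100%.

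**Completers.** The readable text gives no kit size or overage. As an assumption, let spares run from 0 to 34, where 34 is one syringe for each late day of each window (3 + 3 + 7 + 7 + 7 + 7). A completer who takes all 169 doses and returns every spare scores, on the dispensed reading, 169/169 = 100% with no spares and 169/203 = 83.3% with 34.

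**Extra injections.** With 34 spares, a completer who injects 5 extra doses has truly taken 174/169 = 103.0%. That subject returns 29 and scores 174/203 = 85.7% on the dispensed reading.

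**The case against.** Much can be said for leaving this alone. Compliance is a descriptive safety summary. The primary analysis uses the ITT set (SAP 5.1.5). The per-protocol set (SAP 2.1) rests on biopsies, deviations and intercurrent events, with no compliance cut-off in the readable text. SAP 6.1.1 reports exposure duration in bands and SAP 3.1 reports discontinuations with reasons, so the Week 4 stopper would appear in a short-exposure band. Pre-dose PK samples at the on-treatment visits give a separate check on delivered drug. The regimen reading is also strained, since a return count makes most sense against syringes supplied. All of this stands, and it limits the importance of the point. It does not repair the formula: the empty category needs no reading of *prescribed*, and the Day 70 error arises on the natural, dispensed reading without any spare supply.

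Three stronger inferences are tempting, and the documents do not support them.

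- A reader might infer that fully adherent completers are generally marked down. That requires spare syringes, which the documents do not mention. Even at 34 spares, the dispensed reading leaves such a subject at 83%, inside the middle category.
- A reader might infer that the error differs by arm. Protocol 5.2.2 reports the common drug-related adverse events mainly at higher doses in earlier studies, but gives no withdrawal or interruption rates by dose from which to derive a difference.
- A reader might infer that compliance must be rebuilt on the diary, with hold days excluded. Diary against syringe count is a trade-off, because home entries are self-reported and the protocol does not say that daily entries reach the database. Counting interruptions against the scheduled regimen is a legitimate definition. A single approved holiday of at most 5 days (Protocol 8.3) moves the result by about 3 points (5/169 = 3.0%).

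**Conclusion.** The point holds as a minor correction. That the formula cannot exceed 100%, and so contradicts its own top category, is an algebraic certainty. On-treatment compliance is also misstated for early withdrawals who return unused syringes: on the dispensed reading with nominal supply, 83% instead of 100% for an adherent subject who stops on Day 70. On the regimen reading, a Week 4 stopper with nothing to return is shown at 100% after 17% of the planned course. These figures rest on 169 scheduled doses and dispensing in nominal intervals.

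For completers the error is conditional: none without spares, and a score down to about 83% on the dispensed reading if 34 spares are supplied. The consequence stays within a descriptive exposure table. The primary estimand text is not readable in the public SAP, so the statement that nothing else depends on compliance applies to the readable text only.

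**What to change.** Define compliance in SAP 6.1.2 as 100 × (syringes dispensed − syringes returned) / (daily doses scheduled from first dose to last dose). State how unreturned syringes are counted, and cross-check against the diary and observed clinic doses where these are captured.

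Applied to the cases above, the adherent Day 70 subject scores (84 − 14)/70 = 100%, the half-adherent subject (84 − 49)/70 = 50%, and the completer with 5 extra doses (203 − 29)/169 = 103.0%. A fully adherent completer scores 100% whatever the spare supply, provided the spares are returned. All three categories become reachable.

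The cost is a few lines of SAP text and programming, with no new procedure. The remaining weakness is that lost syringes still count as taken unless reconciled: the Day 90 subject who returns nothing would score 126/90 = 140%. The rule for unreturned syringes is therefore needed, or the >100% row will mix extra injections with missing returns.

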#### **6.2** Adverse Events

Adverse events are collected both for the screening/baseline period pre-treatment (which are referred to as pre-treatment AEs) and for the follow-up period after treatment is initiated (which are referred to as post-treatment AEs). All adverse events will be coded using the Medical Dictionary for Regulatory Activities (MedDRA, v23.0).

Treatment emergent adverse events (TEAEs) are defined as AEs that commence on or after the date (and time if available) of first study drug administration. AEs without an onset date or time will be defined as treatment emergent, except if an incomplete date (e.g., month and year) clearly indicates that the event started prior to the start of first administration of study drug or if the AE stop date indicates that the event started or stopped prior to the start of first administration of study drug.

The severity of an AE is rated by National Cancer Institute (NCI) Common Terminology Criteria for Adverse Events (CTCAE) v5. The relationship of an AE to study drug is made using a four-category system: not related, possible, probable, or definite.

The following summary of TEAEs will be provided.

- An overall summary of any TEAEs, any TEAEs leading to study treatment withdrawal, any serious TEAEs, any Aldafermin-related TEAEs, any Rosuvastatinrelated TEAEs, and death
- TEAEs by PT in descending order of incidence
- TEAEs by primary SOC and PT
- TEAEs by primary SOC, PT and severity (CTCAE grade)
- TEAEs by primary SOC, PT and relationship to Aldafermin
- TEAEs by primary SOC, PT and relationship to Rosuvastatin
- TEAEs leading to study treatment withdrawal by primary SOC and PT
- Aldafermin-related TEAEs leading to study treatment withdrawal by primary SOC and PT
- Rosuvastatin-related TEAEs leading to study treatment withdrawal by primary SOC and PT
- Serious TEAEs by primary SOC and PT

A subject will be counted only once within each preferred term and system organ class in the summary tables. The most severe occurrence of a repeat AE, as well as the most extreme relationship of the AE to the study treatment will be used for these analyses. In addition, for the rosuvastatin-related summary tables, only subjects who received rosuvastatin will be included. All SAEs and AEs leading to study drug withdrawal and death will be provided in separate listings.

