2. The primary safety endpoint is frequency, severity, and timing of adverse events (AEs) and serious adverse events (SAEs). Safety and tolerability of aldafermin in subjects with NASH as a function of dose level after up to 24 weeks of treatment with aldafermin will be assessed.

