9.2 Study Visit Procedures

9.2.1 Day -42 (Screening) Procedures

Subjects will report to clinic fasted. The Screening procedures should be all be completed within 42 days from consent in order to randomize the subject.

- Obtain informed consent
- Collect demographic data
- Ascertain medical history
- Collect smoking history
- Assess inclusion/exclusion criteria
- Measure height
- Measure body weight, BMI, waist circumference
- [REDACTED]
- [REDACTED]
- Complete AUDIT-C alcohol consumption questionnaire
- Obtain 12-lead ECG (after subject has been supine for at least 5 minutes)
- Measure vital signs (including temperature, respiratory rate, and seated blood pressure and pulse)
- Register screened subject [REDACTED]
- Record prior and concomitant medications
- Record AEs (starting from the when the subject signs informed consent)
- Obtain blood for 10-hour fasted laboratory sample collection for:
 - Chemistry
 - CBC
 - HbA1c
 - Insulin level
 - HOMA-IR calculation
 - INR
 - Alfa fetoprotein (AFP)
 - Serum pregnancy test (all female subjects of childbearing potential)
 - Hepatitis and HIV screen
 - PEth alcohol screen
 - Lipid panel
- Obtain urine for 10-hour fasted laboratory sample collection for:
 - Urinalysis
 - Urine drug screen

- Subjects with a local historical biopsy will have their slides evaluated and read by the central pathologists to ensure eligibility prior to undergoing MRI-PDFF

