9.2.10 Week 25 (Post-Treatment Response) Procedures

Subjects will report to this visit fasted. The following procedures will be performed at the Week 25 visit:

- [REDACTED]
- Record concomitant medications
- Record new and/or changes to AEs
- Obtain 10-hour fasted clinical laboratory samples for the following:
 - Chemistry
 - INR
 - Lipid panel
 - Lipase
 - C4 and serum bile acids
 - PK sample
 - ADAs
 - NAbs
 - ELF panel

- Pro-C3

■ [REDACTED]

■ [REDACTED]

■ [REDACTED]

Results for ALT, AST, Total Cholesterol, LDL, HDL, and triglycerides are blinded to the site and sponsor.

Before clinic discharge:

- Schedule Week 30 (End of Study) visit

Lipid-Monitoring Assessment:

The third-party Medical Monitor will evaluate LDL-C (refer to [Section 9.4.14](#)). Subjects who have an LDL-C value of > 100 mg/dL, and > 15 mg/dL above their Day 1 value at Week 25 will be re-assessed at Week 30.

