11.1 Definition and Grading Intensity of Adverse Events

An AE is defined as any untoward medical occurrence in a subject of clinical investigational participation administered a pharmaceutical product, whether or not considered drug related. A TEAE is an AE that is reported after a dose of study drug.

AEs include the following:

- Unfavorable changes in general condition
- Subjective or objective signs/symptoms
- Concomitant diseases or accidents
- Clinically relevant adverse changes in laboratory parameters observed in a subject in the course of a clinical study

AEs comprise all disturbances of general health status, subjective and objective disease symptoms (including laboratory abnormalities), and accidents observed in the context of a clinical trial, irrespective of a possible causal relationship with the administration of the trial substance. Events occurring in the framework of a clinical trial during drug-free and post-treatment periods or under placebo are also to be designated as AEs.

All AEs, regardless of how identified (e.g., volunteered, elicited, noted on physical examination), will be recorded throughout the study (i.e., from Screening until Follow-up).

Subjects will be followed for resolution of AEs, by querying the subjects for an ongoing AE until resolved or until any unresolved AEs are judged by the PI to have stabilized or if lost to follow-up. Resolution of all AEs will be promptly documented by the clinic on the subject's CRF.

Any pregnancy diagnosed during the study must be reported immediately to the PI and Sponsor, including pregnancy in female partners of male subjects. The pregnancy will be followed to term and/or outcome and this outcome must be reported to the Sponsor.

Pregnancy, in and of itself, is not regarded as an AE or SAE unless the birth results in a congenital anomaly/birth defect or there is suspicion that the study medication may have interfered with the effectiveness of a contraceptive medication or method.

The PI will rate the severity of AEs using the CTCAE v5 to grade the severity. Each CTCAE v5 term is a Medical Dictionary for Regulatory Activities (MedDRA) Lowest Level Term (LLT). The CTCAE displays Grades 1–5 with unique clinical descriptions of severity for each AE. Not all Grades are appropriate for all AEs. Therefore, some AEs are listed with fewer than five options for Grade selection. Grade 5 (Death) is not appropriate for some AEs and, therefore, is not an option.

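### SAP 6.2 defines a TEAE by onset date alone, so a screening-period event that worsens after dosing can fall outside the TEAE tables, depending on a recording rule the documents do not give

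*SAP*

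**What the plan says.** SAP 6.2 gives the definition used for the tables: "Treatment emergent adverse events (TEAEs) are defined as AEs that commence on or after the date (and time if available) of first study drug administration". Events in the screening or baseline period are collected, "which are referred to as pre-treatment AEs". The list of outputs then opens with "The following summary of TEAEs will be provided" and has ten entries. One of them is "TEAEs by primary SOC, PT and severity (CTCAE grade"); others cover relationship, events leading to withdrawal, and serious events. No table is planned for pre-treatment AEs or for all AEs together.

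Protocol 11.1 words the term differently: "A TEAE is an AE that is reported after a dose of study drug".

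Recording starts before dosing. Protocol 9.2.1 (Day -42) instructs sites: "Record AEs (starting from the when the subject signs informed consent"). Protocol 9.2.10 (Week 25) instructs: "Record new and/or changes to AEs". The same wording stands at Day 1, Week 18 and Week 30.

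Protocol 6.1 sets the endpoint that these tables serve: "The primary safety endpoint is frequency, severity, and timing of adverse events (AEs) and serious adverse events (SAEs"), with safety and tolerability to be assessed by dose level.

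**The concern.** AE collection begins at consent, about six weeks before the first dose, and screening can be extended. Subjects without a usable historical biopsy also have a liver biopsy in that time. Some subjects may therefore reach Day 1 with an AE still ongoing. If that event becomes more severe or serious on study drug, the worsening is safety information about the treatment period. A definition that looks only at when the event began has no place for it.

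At stake is whether the tables describe the endpoint in full. Protocol 6.1 does not limit severity to newly arising events. Protocol 5.2.2 names loose stools, abdominal cramping and nausea among the most common drug-related AEs, seen mainly at higher doses. Symptoms of this kind could already be present in some subjects during screening.

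**Working it through.** No formula in the plan bears on this point, and the documents state no figure for it. The check is a reading of the rules against one case, followed by one line of arithmetic.

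**Step 1: is onset the only test?** Yes. The definition in SAP 6.2 turns on when the AE commences. Its missing-date rule treats an AE with no onset date as treatment emergent, unless partial dates show that it started, or stopped, before first dose. That confirms that a known pre-dose start excludes the event. Neither document has a clause on worsening.

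**Step 2: do all the tables depend on it?** All ten entries in SAP 6.2 are TEAE summaries. The one item not worded as a TEAE is death, within the overall summary. The rule that takes the most severe occurrence of a repeat AE works inside these tables, so it does not bring in an event classed as pre-treatment. Protocol 12.6 also tabulates TEAEs by system organ class and preferred term, and plans no table of other AEs.

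**Step 3: apply the rule to a case.** Suppose an AE starts on Day -10 at Grade 1, is ongoing at Day 1, and reaches Grade 3 at Week 4.

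| How the worsening is recorded | Class under SAP 6.2 | Where it appears |
|---|---|---|
| One record, onset Day -10 | Pre-treatment AE | Listings only |
| New AE line, onset Week 4 | TEAE | TEAE tables and listings |

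**Step 4: which row applies?** The documents do not say. The instruction that separates new AEs from changes to AEs stands at Day 1 (before dosing), Week 18, Week 25 and Week 30. At Weeks 2, 4, 8, 12 and 24 the instruction is to record AEs, without that distinction. The first row is allowed but not required.

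**Step 5: compare the two definitions.** Take an AE that starts before dosing and is first reported at Week 2. It is a TEAE under protocol 11.1, which looks at reporting, and not under SAP 6.2, which looks at onset. The introduction to protocol Section 12 lets the SAP override that section where they differ. The TEAE definition stands in Section 11.1, outside the clause.

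**Step 6: size per subject.** Planned arm size is 38 (protocol Table 3). One subject omitted from a table changes that arm's incidence by 1/38 = 0.026, or 2.6 percentage points. The documents give no rate of AEs ongoing at Day 1 and no rate of later worsening, so the number of such subjects cannot be derived.

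**The case against.** The strongest reply is that the omission depends on a CRF convention that we cannot see. Protocol 11.1 counts unfavourable changes in general condition as AEs, so a site could enter a post-dose worsening as its own AE with a post-dose onset, and SAP 6.2 would count it. This stands, and it is why the point is conditional. It does not remove the gap, because nothing in either document tells sites to do so.

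Second, the loss is from the tables and not from the report. SAEs, and AEs leading to withdrawal or death, are listed without a TEAE restriction, and SAP 2.2 lists all subject-level data. Laboratory values, vital signs, ECGs and injection-site assessments are tabulated by visit whatever the AE class. This also stands, but listings give no incidence by arm.

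Third, the group is narrow. The event must start between consent and first dose, be ongoing at Day 1, worsen, and be kept as one record. A symptom present before consent would have no screening AE record to update, so its worsening would more naturally be entered as a new AE. A reader might infer that a drug which aggravates existing symptoms would have those events removed in general; the documents do not support that.

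Fourth, a reader might infer that the SAP definition affects treatment decisions, because protocol 8.3 acts on Grade 3 or 4 TEAEs. It does not follow: sites work from the protocol, which has its own definition in 11.1.

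Finally, SAP Section 10, on deviations from the protocol, shows a heading without visible text. We cannot say that the difference between the two definitions went unacknowledged.

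**Conclusion.** The point holds as a conditional gap. If a post-dose worsening of a screening AE is kept under its pre-dose onset date, it is left out of every TEAE summary, including those by severity, by relationship and for serious events, and appears only in listings. The one exception is death in the overall summary. Separately, the two TEAE definitions differ, and no clause in the documents settles which one prevails.

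The size is 2.6 percentage points of an arm's incidence per omitted subject, taking 38 per arm as the denominator. The safety set could be slightly smaller. The number of such subjects is unknown.

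Two stronger readings are tempting. One puts a number on the loss. If 10% to 20% of subjects had an AE ongoing at Day 1 and a quarter of these worsened, the count would be 38 × 0.10 × 0.25 = 0.95 to 38 × 0.20 × 0.25 = 1.9 per arm. Those rates have no source in the documents, and they cover any grade increase, so they say nothing about Grade 3 or higher. The other reading is that the dose comparison is biased in favour of the higher doses. That is possible if the drug aggravates screening events more at higher doses, but nothing in the documents shows or quantifies it.

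The sample size and the efficacy analyses are unaffected.

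**What to change.** - **SAP 6.2:** define a TEAE as an AE that starts, increases in CTCAE grade, or becomes serious on or after the first dose of study drug. Tabulate it at its worst post-dose grade and date it at the worsening.
- **CRF instructions:** state how a post-dose worsening of a screening AE is recorded, either as a new line or as a dated grade change on the existing line. The date must be captured in either case. SAP 6.2 counts a subject once per preferred term and system organ class, so a second line would not inflate subject incidence.
- **Protocol 11.1:** reconcile the TEAE definition with the SAP, since the override clause does not reach that section. Protocol 8.3 uses the same term, so the sponsor should check what any change in 11.1 does there; this point takes no position on that rule.

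The cost is a sentence or two in each document and a CRF completion note. If grade changes have not been dated so far, some queries to sites may be needed. The downside is that AE counts may become slightly less favourable.
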